5 STUDY OBJECTIVES AND ENDPOINTS

The objectives of this study are to evaluate the efficacy and safety of tildacerfont in adult subjects with classic CAH who have $A4 \leq 2.5 \times ULN$ and are on supraphysiologic doses of GC therapy (≥ 30 mg/day and ≤ 60 mg/day in HCe) at baseline.

This study will evaluate the potential of tildacerfont to reduce GC burden (total daily GC dose, total GC exposure over 24 weeks) in adult subjects with classic CAH. Study SPR001-204 will characterize clinical outcomes after 1) 24 weeks of double-blind treatment, 2) 52 weeks of open label treatment with tildacerfont and 3) 76 weeks of treatment with tildacerfont to support the clinical relevance of observed changes in GC dose.

The optional Open-Label Extension Period will provide additional characterization of up to 240 weeks of treatment with tildacerfont on GC dose changes and changes in clinical outcomes. See [Table 5](#) for a summary of the study objectives and endpoints.

Table 5 SPR001-204 Study Objectives and Endpoints

Objectives	Endpoints		Analysis
1. Primary Efficacy			
To evaluate the mean absolute GC change in subjects with classic CAH over the 24-week, Double Blind, Placebo-Controlled Treatment Period	1.1	Absolute change from baseline in GC dose in HCe at Week 24	Primary Analysis
2. Secondary Efficacy			
To evaluate the effect of tildacerfont in reducing GC use to near-physiologic levels while maintaining androgen control in subjects with CAH	2.1	Proportion of subjects with GC dose ≤ 11 mg/m ² /day in HCe and $A4 \leq 1.2 \times$ baseline or $A4 \leq ULN$ at Week 24	Primary Analysis
To evaluate the effect of tildacerfont in reducing GC use to near-physiologic levels while maintaining androgen control in subjects with CAH	2.2	Proportion of subjects with baseline GC dose ≤ 35 mg HCe who achieve GC dose ≤ 11 mg/m ² /day in HCe and $A4 \leq 1.2 \times$ baseline or $\leq ULN$ at Week 24	Primary Analysis
To evaluate the effect of tildacerfont in reducing cardiovascular risk in subjects with CAH	2.3	Proportion of subjects with improvement in at least one cardiovascular risk factor at Week 24	Primary Analysis
3. Exploratory Efficacy			
To evaluate the percentage change in GC use in subjects with CAH	3.1	Percent change from baseline in GC dose at Week 24	Primary Analysis

Objectives		Endpoints	Analysis

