5.1.3 Exploratory Efficacy Endpoints

5.1.3.1 Percent Change in HCe Dose at Week 24

Exploratory Efficacy Endpoint 3.1 evaluates the effect of randomized treatment in reducing GC HCe dose in classic CAH subjects at Week 24 in mean percentage terms. This analysis will be achieved by examination of the change in daily GC HCe dose from baseline (Day 1) to post baseline visits on the log scale. Results will be back transformed to present the outcome as a percentage change.

5.1.3.2 Cumulative HCe Dose at Week 24

Exploratory Efficacy Endpoint 3.2 evaluates the effect of randomized treatment in reducing the cumulative HCe dose (total exposure in HCe mg) in classic CAH subjects over 24 Weeks. The endpoint is the cumulative GC dose in HCe from baseline (Day 1) at Week 24. Similar to endpoint 3.1, the endpoint will be analyzed on the log scale.

5.1.3.3 Change in HOMA-IR at Weeks 24 and 52

Exploratory Efficacy Endpoints 3.3 and 3.4 evaluate the effect of randomized treatment in improving HOMA-IR in classic CAH subjects at Weeks 24 and 52. The associated endpoints are the change in fasting HOMA-IR from baseline (Day 1) to Week 24 and Week 52.

5.1.3.4 Improving Cardiovascular Risk Factors at Week 52

Exploratory Efficacy Endpoint 3.5 evaluates the effect of randomized treatment in reducing CV risk factors in classic CAH subjects at Week 52. The endpoint is similar to Secondary Efficacy Endpoint 2.3, being the proportion of subjects who had improvement in at least one CV risk factor at Week 52. Only subjects CV risk factors at baseline will be included in the endpoint analysis.

5.1.3.5 GC use while maintaining androgen control at Week 52

Exploratory Efficacy Endpoints 3.6 and 3.7 are similar to the Secondary Efficacy Endpoints 2.1 and 2.2, but now assessed at 52 weeks. Secondary Efficacy Endpoints 3.6 is the response to randomized treatment in terms of reducing GC to $\leq 11\text{mg mg/m}^2/\text{day}$ in HCe while maintaining

androgen control, defined as A4 levels at approximately baseline ($\leq 1.2x$ baseline) or within normal limits (\leq ULN) at Week 52 in subjects with CAH.

Exploratory Efficacy Endpoint 3.7 is similar to 3.6 but evaluated in those subjects with baseline GC ≤ 35 mg/m²/day in HCe.

5.1.3.6 Quality of Life at Week 24 and Week 52

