8.3.20.4 Stress Event

A stress event is defined as an entry in the diary indicating a stress dose was taken or a record in the CM eCRF if the stress dosing was not recorded in the diary in a timely manner. Consecutive days of stress dosing are counted as a single stress event.

8.3.20.5 Cumulative GC Dose at Week 24

The cumulative GC dose from Study Day 1 to Week 24 is defined as:

- Sum of daily GC exposures (total daily dose multiplied by days on a regimen) from CM eCRF
- Sum of stress doses (HCe mg) (from CM eCRF where the indication for the stress dosing is “STRESS DOSE/DOSING”)

For subjects who discontinue study drug treatment prior to the Week 24 visit, the cumulative dose will be summed over the duration of Study Day 1 to the date of last dose of study drug.

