8.3.21.1 Concomitant Medications

A concomitant medication (CM) is considered to be any medication that is continued during Screening through last dose +24 hours.

CMs that stop prior to the first dose of study drug will be reported as screening concomitant medications and will be summarized with the prior medications.

CMs that are continued after the first study drug dosing, or with start dates or stop dates post first dose of study drug through last dose date + 24 hours, missing CM end date, or ongoing are considered on-treatment CMs.

Post medications is considered to be any medication taken after the last study drug dose date + 24 hours, missing CM end date, or ongoing.

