9.6 Type I Error Control

Type I Error control for the Secondary Efficacy Endpoints will be achieved by hierarchical testing. If the Primary Efficacy Endpoint is met, then Secondary Efficacy Endpoints displayed in [Table 5](#) will be evaluated using the Hochberg (1988) closed test procedure with an alpha of 0.05.

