12.3.3.1 Multiple Imputation for the Primary Efficacy Endpoint Analysis

Missing data can have an adverse effect on the estimation of endpoints. As such, multiple imputation for missing data will be used for the Primary Efficacy Endpoint analysis. Imputation will be performed under the assumption of missing at random (MAR) and supported by contemporary imputation under the assumption of missing not at random (MNAR). In addition, retrieved drop-out based multiple imputation will be explored whereby data from subjects who prematurely discontinue study drug treatment but remain in the study and still have assessments collected at the remaining scheduled visits in the study as used as the basis for imputation.

Thus, in the event of missing GC HCe values at Weeks 3, 6, 12 18 and 24, data will be imputed as follows:

(a) MAR Imputation

Step 1: Non-monotone missing data will be imputed first based on the MAR assumption via a multivariate joint Gaussian imputation model using Markov chain Monte Carlo (MCMC) method using the MCMC statement in the SAS® PROC MI procedure. Twenty imputed datasets will be produced. As a result, each imputed dataset will only have missing data at the end of subjects' records, (i.e. a monotone missing data pattern). The MCMC method in the MI procedure will be used with multiple chains (option CHAIN=MULTIPLE), 100 burn-in iterations, and a non-informative prior to imputed the remaining missing data. A separate imputation model will be used for each treatment arm. The imputation models will include GC HCe values at baseline and Weeks 3, 6, 12 and 18, sex, baseline GC type and baseline and CAH Type. In case

of non-convergence or non-estimability issues, a ridge prior and a single model will be considered with treatment arm added as explanatory variable to the model.

Step 2: The remaining, monotone, missing data for all subjects who discontinue study prematurely will be imputed using sequential regression multiple imputation model by randomised treatment arm. Each sequential regression model (i.e., for imputation of values at a given time point) will include the same explanatory variables as in Step 1 and all prior GC HCe values.

Step 3: The change from baseline in GC HCe to each scheduled post-baseline visit will be calculated, based on observed and imputed data. Each of the imputed complete datasets from Step 2 will be analysed with the same MMRM model used for the Primary Efficacy Endpoint ([Section 12.3.3](#)).

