12.6.4 Exploratory Efficacy Endpoint 3.2, Cumulative GC Dose

Cumulative GC dose in HCe over the period baseline to 24 weeks from randomization will be analysed via ANCOVA on the log scale. The model will include log cumulative GC dose in HCe over baseline to 24 weeks as the dependent variable; treatment group (0: placebo, 1: tildacerfont); the randomization strata: sex (0: male, 1: female) and baseline GC dose (in HCe, 0: < 40 mg/day, 1: ≥ 40 mg/day); and baseline GC type (0: short-acting, 1: intermediate-acting or combination) as categorical explanatory variables. The difference in LSmeans between

randomised treatment groups along with the associated CI and p-value will be extracted. The LSmeans and CI will be back transformed for the purposes of presentation.

The descriptive statistics in terms of the cumulative GC dose will be reported by treatment group and will include the geometric mean, log scale SE, Q1, Q3, min and max.

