12.6.4.1 Sensitivity Analyses: Completers

In order to further evaluate the impact of early discontinuation on GC exposure, the cumulative GC dose in HCe analysis at 24 weeks will be repeated using only subjects who completed the full 24 weeks of treatment.

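### Cumulative GC dose (endpoint 3.2) is cut off at the last study-drug dose for early discontinuers, so stopping study drug counts as a GC saving

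*SAP*

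**What the plan says.** SAP 5 counts "total GC exposure over 24 weeks" as part of the GC burden the study is to reduce. SAP 5.1.3.2 describes endpoint 3.2 as the effect of treatment in "reducing the cumulative HCe dose (total exposure in HCe mg) in classic CAH subjects over 24 Weeks". SAP 12.6.4 gives the same period: "Cumulative GC dose in HCe over the period baseline to 24 weeks from randomization will be analysed via ANCOVA on the log scale". The model terms there are treatment, sex, baseline GC dose stratum and baseline GC type. SAP 12.6 sets the population as ITT.

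SAP 8.3.20.5 defines the variable as daily GC exposure plus stress doses from Study Day 1 to Week 24, then adds an exception. If study drug is stopped early, before Week 24, the rule is that "the cumulative dose will be summed over the duration of Study Day 1 to the date of last dose of study drug".

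The one safeguard specific to 3.2 is SAP 12.6.4.1, which repeats the analysis in subjects who completed 24 weeks of treatment. Its stated purpose begins "In order to further evaluate the impact of early discontinuation on GC exposure". Endpoint 3.2 is not among the endpoints listed for missing-data sensitivity analyses in SAP 12.6.1.1.

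**The concern.** GC replacement in CAH is lifelong (Protocol 2.2.2), so GC intake does not end when study drug ends. The exception therefore drops real exposure from the total. Partial sums over a few weeks are analysed beside full 24-week sums, with no covariate, offset or per-day scaling to make them comparable. A low total can mean a lower GC dose or simply an early stop, and the analysis cannot tell the two apart.

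If stopping is more frequent or earlier on tildacerfont, for example through the liver, QT, psychiatric or adrenal-insufficiency criteria in Protocol 7.1, a tolerability problem would be reported as GC sparing. If it is more frequent or earlier on placebo, a real saving would be hidden.

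The rule is also out of line with the rest of the SAP. The primary estimand (12.3.1) ignores treatment discontinuation, and 12.3.3.1 plans to draw on data from "subjects who prematurely discontinue study drug treatment but remain in the study and still have assessments collected at the remaining scheduled visits".

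**Working it through.** The plan states no effect size, power or discontinuation rate for endpoint 3.2, so there is no figure of its own to reproduce.

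**Single subject.** Total = daily dose × days summed, with 24 × 7 = 168 days for the full period and stress doses left out. At a constant 35 mg/day:

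- completer: 35 × 168 = 5,880 mg
- study drug stopped at Day 42: 35 × 42 = 1,470 mg
- apparent saving: 1 − 1,470/5,880 = 75%

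At any constant dose the apparent saving is 1 − (stop day)/168: 75%, 50% and 25% for stops at Days 42, 84 and 126.

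**Comparison with the fastest 5 mg reduction.** Take a completer who reduces by 5 mg at each of Weeks 2, 6, 12 and 18, with the 15 mg floor (SAP 4.2.2.1). From 40 mg/day the total is 40×14 + 35×28 + 30×42 + 25×42 + 20×42 = 4,690 mg, against 40 × 168 = 6,720 mg unchanged, a saving of 30%. The same sum gives 3,220 against 5,040 mg (36%) from 30 mg/day and 8,050 against 10,080 mg (20%) from 60 mg/day. Dividing by the starting dose (3,220/30, 4,690/40, 8,050/60), a subject with no reduction at all who stops before about Day 107, 117 or 134 scores better than that completer.

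**Group level, no true effect.** With a common stop day s and an excess proportion p stopping in one arm, the false geometric mean ratio is (s/168)^p. For s = 84 it is 0.966, 0.933 and 0.871 at p = 5%, 10% and 20%.

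**Simulation of the 12.6.4 ANCOVA.** 45 per arm, 4,000 trials per scenario, no true effect. Assumed: baseline 30–60 mg/day; 5 mg steps about two weeks after Day 1 and Weeks 6, 12 and 18 (22% chance of a reduction at each, 7% chance of an increase from Week 6); floor 15 mg; stops independent of dose and uniform over Days 14–126 unless stated.

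| Stopping, tildacerfont v placebo | Rejection, truncated total | Mean spurious difference |
|---|---|---|
| 10% v 5% | 9.2% | −5% |
| 15% v 5% | 22.1% | −9% |
| 20% v 5% | 41.4% | −14% |
| 10% v 10%, Days 14–56 v 85–126 | 21.6% | −11% |
| 10% v 10%, same timing | 4.5% | none |

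With equal 10% stopping and the same timing, the standard error on the log scale is 0.078 against 0.029 for the full sum (0.078/0.029 = 2.7). Summing to Day 168 gives 4.5–5.2% rejection and no bias in every scenario. The completers analysis gives 4.4–5.3%, but only because stopping was assumed unrelated to dose. Monte Carlo error is 0.3–0.8 percentage points.

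**A second simulation with simpler assumptions.** 2,000 trials, baseline uniform 30–60 mg/day, average dose varying around baseline with SD 4 mg/day, stop days uniform over 28–154. Truncation gives 7.8%, 17.6% and 34.6% rejection for 10%, 15% and 20% v 5%; full summation gives 4.1–5.4% across the scenarios run. With 5% v 15% (more stopping on placebo), a true 3 mg/day effect is detected in 5.8% of trials under truncation and 62% under full summation. With equal 10% stopping the figures are 22% and 62%.

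**The case against.** The strongest reply is that little hangs on this. Endpoint 3.2 is one of 20 exploratory endpoints. In SAP 9.6, "Type I Error control for the Secondary Efficacy Endpoints will be achieved by hierarchical testing", and 3.2 is outside that scheme. The primary MMRM and endpoint 3.1 carry the GC-reduction message without truncation, and 12.6.4.1 shows that the authors saw the problem. This stands as a limit on severity. It does not correct the main 3.2 result, which is reported with a confidence interval and p-value. The completers analysis also selects on a post-randomisation event.

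Second, the bias is conditional and every rejection rate rests on assumed stopping. This stands. Protocol 7.2 expects withdrawal to be uncommon, but that refers to leaving the study, whereas truncation is triggered by stopping study drug. The rates illustrate the size; the false saving for each affected subject does not depend on them.

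Third, the repair needs data and rules that are not fully in place. Protocol 7.1 promises continued collection only when possible, and also calls for an early termination visit. SAP 12.3.3.1 imputes visit values rather than daily doses, offers several methods, and says the retrieved-dropout method will only be explored. The simulated full sum assumed GC was known on every day; imputation after study exit was not simulated. Carrying the last dose to Day 168 was run as a missing-data illustration and gave 4.6–5.5% rejection with bias of at most 0.3%. These points mean the rule must be spelled out. They do not justify truncation, and imputation matters only for subjects who leave the study.

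Fourth, average daily dose over observed days needs no imputation and showed bias of at most 0.5%. It is a reasonable supportive measure, but it is not 24-week exposure.

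**Conclusion.** The concern holds. SAP 8.3.20.5 contradicts the 24-week exposure that sections 5, 5.1.3.2 and 12.6.4 set out to measure, and nothing in the SAP repairs the main analysis. The artefact at subject level is certain wherever GC continues after study drug stops: 75%, 50% or 25% for stops at Days 42, 84 or 126 on a constant dose.

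Between-arm bias arises only if the amount or timing of stopping differs, and it can favour either arm. Under the assumed rates, false-positive rates run from about 9% to 41% in the first simulation and 8% to 35% in the second. With equal stopping there is no bias, only a large loss of precision.

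This should be corrected before the Week 24 lock. Because 3.2 is exploratory, the harm is a misleading GC-burden result in the study report.

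**What to change.** - Delete the truncation sentence in SAP 8.3.20.5. Sum prescribed GC and stress doses from Day 1 to Week 24 (Day 168) for every ITT subject regardless of study-drug status.
- State that GC records after the last study-drug dose count towards the total, because SAP 8.3.21.1 would otherwise set them apart: "Post medications is considered to be any medication taken after the last study drug dose date + 24 hours".
- For days after study exit, use GC doses imputed under 12.3.3.1. Name the method, and say how visit values become daily doses, for example by holding each imputed value until the next visit.
- Keep the log-scale ANCOVA of the 24-week total as the main analysis. Report log average daily dose over observed days, and the completers analysis, as supportive.
- While rewriting the definition, check that stress days are not counted twice. Protocol 4.1.4.4 says stress doses replace the usual daily dose, whereas 8.3.20.5 adds the two sums. This is a separate, existing issue.

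The cost is SAP wording and modest programming, plus running the ANCOVA on the imputed datasets and pooling the results if any subjects leave the study. Post-discontinuation GC records may be incomplete, so the report should give the number of subjects and days imputed in each arm.

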8.3.21 Concomitant and Prohibited Medications

All medication verbatim terms reported on the eCRFs will be mapped according to the World Health Organization (WHO) Drug Dictionary (WHO DD March 2020 B3). The medications will be mapped to Anatomical/Therapeutic/Chemical (ATC) class and preferred names.

A prior medication is considered to be any medication that is taken within a year prior to screening.

8.3.21.1 Concomitant Medications

A concomitant medication (CM) is considered to be any medication that is continued during Screening through last dose +24 hours.

CMs that stop prior to the first dose of study drug will be reported as screening concomitant medications and will be summarized with the prior medications.

CMs that are continued after the first study drug dosing, or with start dates or stop dates post first dose of study drug through last dose date + 24 hours, missing CM end date, or ongoing are considered on-treatment CMs.

Post medications is considered to be any medication taken after the last study drug dose date + 24 hours, missing CM end date, or ongoing.

8.3.21.2 Prohibited Concomitant Medications

Prohibited and cautionary concomitant medications are those medications with their potential for metabolic interactions with tildacerfont. Specific definitions can be found in Protocol Sections 6.5.1 and 13.1.

8.3.22 Treatment-Emergent Adverse Events

All AE verbatim terms reported on the eCRFs will be coded using the Medical Dictionary for Regulatory Activities (MedDRA® version 23.0). Treatment-emergent adverse events (TEAEs)

are defined as any AEs that have an onset or worsening in severity on or after the first dose of double-blinded study drug until 30 days after the last dose of study drug. Non-TEAEs include those events occurred during the screening and/or GC conversion Period and after 30 days of the last dose of study drug. Non-TEAEs will be listed in AE listings but excluded from TEAE summaries.

Related AEs are those reported by investigators as possibly related, probably related, or definitely related to the study drug or GC regimen.

AESIs are events that do not meet SAE criteria but must be monitored on an ongoing basis as defined in Protocol Section 8.3.8 and identified in the AE eCRF page. Serious AEs (SAEs) are defined according to the National Cancer Institute Common Terminology Criteria for Adverse Events (CTCAE 2017) version 5.0, as described in Protocol Section 8.3.3.1. Adverse events

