6 STUDY INTERVENTION

6.1 Study Intervention Administration

6.1.1 Study Intervention Description

Tildacerfont is a small-molecule CRF₁ receptor antagonist.

Details about the physical, chemical, and pharmaceutical properties of tildacerfont are provided in the IB.

Study drug is defined as either tildacerfont or placebo.

Study treatment is defined more broadly as study drug, GC regimens, or HC for stress dosing provided by the Sponsor.

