8.3.3.2 Relationship to Study Drug or Study Glucocorticoid (Study Treatment)

The Investigator will assess the relationship of each AE separately to study drug and to the study GC according to the categories in [Table 5](#). This assessment will serve to determine whether there exists a reasonable possibility that the study drug or study GC caused or contributed to the AE.

Table 5. Relatedness of Adverse Event to Study Drug or Study Glucocorticoid

UNRELATED: This category applies to those AEs that are clearly and incontrovertibly due to extraneous causes (disease, environment, etc).
UNLIKELY RELATED: This category applies to those AEs that are judged to be unrelated to study treatment but for which no extraneous cause may be found. An AE may be considered unlikely to be related to study treatment if or when it meets two of the following criteria : (1) it does not follow a reasonable temporal sequence in relation to administration of study treatment; (2) it could readily have been produced by the subject's clinical state, environmental or toxic factors, or other therapies administered to the subject; (3) it does not follow a known pattern of response to study treatment; or (4) it does not reappear or worsen when study treatment is re-administered.
POSSIBLY RELATED: This category applies to those AEs for which a connection to study treatment administration cannot be ruled out with certainty. An AE may be considered possibly related if or when it meets two of the following criteria : (1) it follows a reasonable temporal sequence in relation to administration of study treatment; (2) it could not readily have been produced by the subject's clinical state, environmental or toxic factors, or other therapies administered to the subject; or (3) it follows a known pattern of response to study treatment.

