PROBABLY RELATED: This category applies to those AEs that the Investigator thinks are related to study treatment with a high degree of certainty. An AE may be considered probably related if or when it meets three of the following criteria : (1) it follows a reasonable temporal sequence in relation to administration of study treatment; (2) it could not be reasonably explained by the known characteristics of the subject's clinical state, environmental or toxic factors, or other therapies administered to the subject; (3) it disappears or decreases on cessation or reduction in dose of study treatment. There are exceptions when an AE does not disappear upon discontinuation of study treatment yet treatment-relatedness clearly exists (e.g., as in bone marrow depression, fixed drug eruptions, or tardive dyskinesia); or (4) it follows a known pattern of response to study treatment.
DEFINITELY RELATED: This category applies to those AEs that the Investigator thinks are incontrovertibly related to study treatment. An AE may be assigned an attribution of definitely related if or when it meets all of the following criteria : (1) it follows a reasonable temporal sequence in relation to administration of study treatment; (2) it could not be reasonably explained by the known characteristics of the subject's clinical state, environmental or toxic factors, or other therapies administered to the subject; (3) it disappears or decreases upon cessation or reduction in dose of study treatment and recurs with re-exposure to study treatment (if rechallenge occurs); and (4) it follows a known pattern of response to study treatment.

Abbreviation: AE, adverse event.

The Investigator will use clinical judgment and consult the IB to determine the relationship. Alternative causes, such as underlying disease(s), concomitant therapy, and other risk factors, as well as the temporal relationship of the event to study drug or study GC administration will be considered and investigated.

AEs classified as unrelated or unlikely related to study treatment will be considered not related to treatment, and AEs classified as possibly, probably, or definitely related to study treatment will be considered related to treatment.

8.3.3.3 *Outcome*

The outcome of each AE will be recorded as one of the categories in [Table 6](#).

Table 6. Outcome of Adverse Event

Not recovered/not resolved: The event has not improved or recuperated.

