9.4.7.3 Adverse Event Data

AEs will be coded using the Medical Dictionary for Regulatory Activities (MedDRA). AE summaries will be presented by System Organ Class, Preferred Term, severity, and frequency and percentage of subjects reporting each observed event.

AEs that occur before the first dose of study drug will be distinguished from TEAEs (defined in [Section 8.3.1](#)). All AEs and TEAEs will be listed by subject. The frequency of subjects who experience TEAEs will be summarized overall and by treatment group. TEAEs will also be summarized by relationship to study drug and severity.

Listings will be provided for subjects who experienced an SAE or discontinued study drug/withdrew from the study because of an AE.

9.4.7.4 *Laboratory Data*

Clinical laboratory test results will be listed by subject. Reference ranges provided by the laboratory for each parameter will be used to evaluate the clinical significance of laboratory test results. Values outside the relevant reference range will be flagged in the listings. Abnormal clinical laboratory test results will be listed in a separate listing.

Laboratory data will be summarized in terms of observed values, changes from baseline, values relative to normal ranges, and changes from baseline relative to normal ranges. Subjects meeting specific thresholds for laboratory data will also be summarized as specified in the SAP.

P-values for change from baseline and change from placebo or differences in proportions meeting specific thresholds will be derived using the appropriate statistical test as specified in the SAP.

Additional subgroup analyses based on baseline laboratory data [elevated, normal] will be specified in the SAP.

9.4.7.5 *Vital Signs Data*

Vital signs data will be summarized within appropriately defined categories in terms of observed values (by time point), changes from baseline (by time point), and counts and percentages. Subjects meeting specific thresholds for vital sign data will also be summarized as specified in the SAP.

P-values for change from baseline and change from placebo will be derived using t-tests as specified in the SAP.

9.4.7.6 *ECG Data*

The QTcF, PR interval, QT interval, QRS duration, and heart rate from standard digital ECGs will be summarized within appropriately defined categories in terms of observed values, changes from baseline, and counts and percentages.

9.4.7.7 *Psychiatric Evaluations*

C-SSRS and HADS data will be listed.

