13.1.2 Summary of TEAEs by System Organ Class and Preferred Term

In addition, TEAEs will be summarized by MedDRA SOC and PT. Each summary table will be presented by study period (i.e., Placebo-Controlled Treatment, and Open-Label Treatment) and treatment group as well as overall by treatment group. A subject experiencing multiple occurrences of an adverse event will be counted only once for each PT. Subjects with multiple PTs within a SOC will be counted only once for that SOC. The summaries will be presented for

the following; if a summary does not include more than 20 events, summaries by PT only (Section 13.1.3) may be deemed to be sufficient:

- TEAEs by SOC and PT
- Severe TEAEs by SOC and PT
- Study drug-related TEAEs by SOC and PT
- Severe Study drug-related TEAEs by SOC and PT
- AESIs by SOC and PT
- AESI of liver Events
- Serious TEAEs by SOC and PT
- Serious Study drug-related TEAEs by SOC and PT
- TEAEs leading to study drug discontinuation by SOC and PT
- TEAEs leading to death by SOC and PT

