13.1.3 Summary of TEAEs by Preferred Term

In addition, TEAEs will be summarized by MedDRA PT. Each summary table will be presented by study period (i.e., Placebo-Controlled Treatment, and Open-Label Treatment) and treatment group as overall by treatment group. A subject experiencing multiple occurrences of an adverse event will be counted only once for each PT. The summaries will be presented for:

- TEAEs by PT
- Severe TEAEs by PT
- Study drug-related TEAEs by PT
- Severe Study drug-related TEAEs by PT
- AESIs by PT
- Serious TEAEs by PT
- Serious Study drug-related TEAEs by PT
- TEAEs leading to study drug discontinuation by PT
- TEAEs leading to death by PT

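### SAP 8.3.22 defines a related AE by study drug or GC regimen together, so events attributed only to GC could enter the study drug-related tables

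*SAP*

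**What the plan says.** The SAP defines relatedness once, in 8.3.22: "Related AEs are those reported by investigators as possibly related, probably related, or definitely related to the study drug or GC regimen". It has no separate definition of study drug-related.

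The Protocol keeps the two causes apart:

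- Section 8.3.3.2: "The Investigator will assess the relationship of each AE separately to study drug and to the study GC".
- Section 6.1.1: "Study drug is defined as either tildacerfont or placebo". The wider term is distinct: "Study treatment is defined more broadly as study drug, GC regimens, or HC for stress dosing provided by the Sponsor".
- Section 8.3.3.2, on collapsing the causality categories: "AEs classified as possibly, probably, or definitely related to study treatment will be considered related to treatment". This rule uses the wider term.
- Section 9.4.7.3, on reporting: "TEAEs will also be summarized by relationship to study drug and severity".

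The SAP's relatedness tables carry the narrower label. Section 13.1.2 lists "Study drug-related TEAEs by SOC and PT" and Section 13.1.3 lists "Study drug-related TEAEs by PT", each with a severe and a serious version. That makes six tables. SAP 13.1 (highest relationship for a repeated event) and SAP 9.3.3.1 (imputation of missing causality) both refer to relationship to study drug only.

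**The concern.** A definition of related that joins the two causality answers with an 'or' does not match tables labelled by study drug. An event judged unrelated to tildacerfont or placebo but possibly related to the GC regimen is related under 8.3.22. It is not study drug-related under the Protocol's terms. A programmer who builds the flag from 8.3.22 and one who builds it from the table titles would produce different safety tables from the same plan.

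This matters more here than in most trials. GC dose is the primary endpoint, and SAP Section 6 powers the trial for between-arm differences of 5 and 7.25 mg/day HCe. Protocol 7.1.5 anticipates adrenal insufficiency from GC undertreatment. Whether an event is put down to the drug or to the GC regimen is therefore a real safety question, and the two separate ratings are the data that address it.

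**Working it through.** There is no figure in the plan to reproduce. The check compares the texts, then illustrates the effect with assumed rates.

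**Step 1: which variable does each place point to?**

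| Place | Basis of relatedness |
|---|---|
| SAP 8.3.22 (definition) | study drug or GC regimen |
| SAP 13.1 (repeated events) | study drug |
| SAP 9.3.3.1 (missing causality) | study drug |
| SAP 13.1.2 and 13.1.3 (six table titles) | study drug |
| Protocol 8.3.3.2 (collection) | study drug and study GC, separately |
| Protocol 8.3.3.2 (collapse rule) | study treatment, which under 6.1.1 includes GC regimens |
| Protocol 9.4.7.3 (summaries) | study drug |

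The pooled wording stands alone in the SAP, but it is the only sentence there that defines the term.

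**Step 2: does another provision settle it?** SAP Section 3 lets the SAP govern where it differs from the Protocol on planned analyses. The Protocol's wording therefore does not cure the definition. That rule does not choose between two readings within the SAP. SAP Section 14, where a deliberate departure would be recorded, is still marked as to be determined.

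**Step 3: what would pooling do?** Let d be the proportion of subjects with a drug-attributed TEAE, and g the proportion with a TEAE attributed only to GC. The documents give neither, so both are assumed, and the two are taken as independent.

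- Pooled rate in an arm = 1 - (1 - d)(1 - g)
- Between-arm difference when d is equal = (1 - d) × (g tildacerfont - g placebo)

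With d = 10% in both arms, so that the true drug-related difference is 0:

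| GC-only rate, placebo v tildacerfont | Pooled rate, placebo | Pooled rate, tildacerfont | Difference |
|---|---|---|---|
| 5% v 5% | 1 - 0.90 × 0.95 = 14.5% | 14.5% | 0 |
| 5% v 15% | 14.5% | 1 - 0.90 × 0.85 = 23.5% | +9.0 points |
| 15% v 5% | 23.5% | 14.5% | -9.0 points |

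The assumed d matters little. For 5% v 15%, d = 5% gives 0.95 × 10 = +9.5 points and d = 20% gives 0.80 × 10 = +8.0 points. A drug-only flag gives 0 in every row. In the equal-rate row the between-arm difference is right, but each arm's drug-labelled rate is 14.5% where the drug-only rate is 10%.

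**The case against.** The best defence is that 8.3.22 defines related, not study drug-related. On that reading the sentence only says which causality grades count as related, for whichever of the two questions is being asked. The six tables then use the study-drug answer, as their titles and SAP 13.1 and 9.3.3.1 suggest. This is a plausible reading, and it is why the point is an inconsistency rather than proof of a pooled analysis. It does not remove the problem: a literal application of the only stated definition gives the other result.

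Three stronger conclusions might be inferred, and the documents do not support them.

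- **That the tables will be pooled.** The drug-only wording elsewhere in the SAP points the other way. The mock shells (Appendix A, cited in SAP Section 8), which might settle it, are not in the documents reviewed.
- **That the two causes could not be separated.** Both ratings are collected, and SAP 13.1 lists all reported AEs. At most a summary is missing. No GC-related table appears in the SAP text, but the Protocol does not ask for one.
- **That tildacerfont would show a false excess.** Both arms follow the same A4 algorithm (Protocol 4.1.4.3), so GC can move either way in either arm. A larger taper could bring more events attributed to GC change. Equally, Protocol 2.2.2 describes harms of high GC doses, so a lower dose could bring fewer.

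The reach is also limited. TEAE tables not based on relatedness (all, severe, serious, AESI, discontinuation, death) are unaffected, as are efficacy and Type I error.

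**Conclusion.** The point holds as a conflict in the plan's definitions. SAP 8.3.22 pools two causes that the Protocol has rated separately and that the rest of the SAP labels as study drug alone. If the flag is derived from 8.3.22, events attributed only to GC enter all six study drug-related tables. The size and sign of any between-arm distortion are unknown. The range of -9.0 to +9.0 points comes from assumed rates and independence; it shows what the wording permits and does not predict what will occur. The wording should be corrected before unblinding, because it governs headline safety tables and the correction is nearly free.

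**What to change.** In SAP 8.3.22:

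1. Define study drug-related as possibly, probably or definitely related on the study-drug causality answer alone, and state that all study drug-related tables in 13.1.2 and 13.1.3 use this flag.
2. Define GC-related in the same way from the GC answer. Optionally, tabulate it separately by arm and study period.
3. If a combined category is kept, label it study treatment-related, in line with Protocol 6.1.1.

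The cost is a few lines of SAP text and, if wanted, one or two extra tables. No new data are needed, since the Protocol already requires both ratings.
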